7.7 Other Anti-Cancer Treatments and Tobacco Smoking History During Follow-up

Patients may receive surgical, systemic or radiation treatments for cervical cancer other than the protocol surgery and adjuvant treatments given 4 weeks within the protocol surgery treatment or smoke tobacco during the follow-up.

- Any surgery/procedure given 4 weeks after the surgery but before the first pelvic recurrence (reported on Follow Up Report) : yes, no (**Table 39**)
- Type and reason for surgery/procedure given 4 weeks after the surgery but before the first pelvic recurrence (reported on Follow Up Report) (**Table 39**)
- Any surgery/procedure given after the first pelvic recurrence (reported on Short Follow Up Report): yes, no (**Table 39**)
- Type and reason for surgery/procedure given after the first pelvic recurrence (reported on Short Follow Up Report) (**Table 39**)
- Any other anti-cancer treatment given 4 weeks after the surgery but before the first pelvic recurrence (reported on Follow Up Report): yes, no (**Table 40**)
- Type and treatment name or site for other anti-cancer treatment given 4 weeks after the surgery but before the first pelvic recurrence (reported on Follow Up Report) (**Table 40**)
- Any other anti-cancer treatment given after the first pelvic recurrence (reported on Short Follow Up Report): yes, no (**Table 40**)

- Type and treatment name or site for other anti-cancer treatment given after the first pelvic recurrence (reported on Short Follow Up Report) (**Table 40**)
- Smoked tobacco 4 weeks after the surgery but before the first pelvic recurrence (reported on Follow Up Report): yes, no (**Table 41**)
- Smoked tobacco after the first pelvic recurrence (reported on Short Follow Up Report): yes, no (**Table 41**)

7.8 Patient Reported Outcomes

The patient report outcomes (PROs) of patients in this study include the quality of life assessed by using EORTC QLQ-C30 (version 3.0) with module QLQ-CX24 and sexual health by the Female Sexual Function Index (FSFI) and the Female Sexual Distress Scale (FSDS-R) before randomization (baseline), at 3 months, 6 months, 12 months, 24 months, 36 months after the surgery but before the first pelvic recurrence, and at the time of the first recurrence. The following are the scoring algorithms for EORTC QLQ-C30, EORTC QLQ-CX24, FSFI and FSDS-R with Q_i denoting the i -th question in the PRO questionnaire.

7.8.1 Scoring Algorithms

7.8.1.1 EORTC QLQ-C30

The EORTC core questionnaire, QLQ-C30 (version 3.0), consists of five Functional Scales, one Global Health Status, and nine Symptoms Scales. Each scale in the questionnaire will be scored (0 to 100) according to the EORTC recommendations in the EORTC QLQ-C30 Scoring Manual. The scoring method for EORTC QLQ-C30 is summarized below.

Functional scales:

- Physical functioning: $(1 - ((Q1+Q2+Q3+Q4+Q5)/5 - 1)/3) * 100$
- Role functioning: $(1 - ((Q6+Q7)/2 - 1)/3) * 100$
- Emotional functioning: $(1 - ((Q21+Q22+Q23+Q24)/4 - 1)/3) * 100$
- Cognitive functioning: $(1 - ((Q20+Q25)/2 - 1)/3) * 100$
- Social functioning: $(1 - ((Q26+Q27)/2 - 1)/3) * 100$

Global health status:

- Global health status: $((Q29+Q30)/2 - 1)/6 * 100$

Symptom scales:

- Fatigue $((Q10+Q12+Q18)/3 - 1)/3 * 100$
- Nausea and vomiting $((Q14+Q15)/2 - 1)/3 * 100$
- Pain $((Q9+Q19)/2 - 1)/3 * 100$
- Dyspnea $((Q8 - 1)/3) * 100$
- Insomnia $(Q11 - 1)/3 * 100$
- Appetite loss $(Q13 - 1)/3 * 100$
- Constipation $(Q16 - 1)/3 * 100$
- Diarrhea $(Q17 - 1)/3 * 100$
- Financial difficulties $(Q28 - 1)/3 * 100$

7.8.1.2 EORTC QLQ-CX24

The EORTC Cervical Cancer Module, QLQ-CX24, consists of three multi-items scales: symptom experience, body image, and sexual/vaginal functioning and five single items pertaining to menopausal symptoms, lymphedema, lower back pain, tingling and numbness and sexual enjoyment. The following are the scoring algorithms for these scales and items of EORTC QLQ-CX24:

- Symptom Experience $((Q31+...+Q37+Q39+Q41+...+Q43)/11-1)/3 * 100$
- Body Image $((Q45+...+Q47)/3-1)/3 * 100$
- Sexual/Vaginal Functioning $((Q50+...+Q53)/4-1)/3 * 100$
- Lymphoedema $(Q38-1)/3 * 100$
- Peripheral Neuropathy $(Q40-1)/3 * 100$
- Menopausal Symptoms $(Q44-1)/3 * 100$
- Sexual Worry $(Q48-1)/3 * 100$
- Sexual Activity $(1 - (Q49-1)/3) * 100$
- Sexual Enjoyment $(1 - (Q54-1)/3) * 100$

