2.5.4 Quality of Life Instruments

The relative impact of surgery on pelvic symptoms will be evaluated with the 24-item Cervical Cancer Module (**EORTC QLQ-CX24**), which has three multi-item subscales: Symptom Experience, Body Image, and Sexual/Vaginal functioning, and five single items pertaining to menopausal symptoms, lymphedema, lower back pain, tingling and numbness, and sexual enjoyment. Higher scores correspond to worse symptoms except for items 49 and 54. Specifically, we will focus on the Symptom Experience subscale, which includes items pertaining to difficulty with bowel, bladder, and vaginal symptoms, and items can be analyzed separately. The QLQ-CX24 discriminates well between patient subgroups on the basis of treatment modality as well as stage of disease and is available in a variety of languages [Greimel 2006]. Cronbach's alpha ranges from 0.72-0.87 for the multi-item domains.

In addition to this module, the core questionnaire, the EORTC QLQ-C30, will be administered. This is a well validated 30-item questionnaire consisting of five function scales (physical, role, emotional, cognitive, and social), three symptom scales (fatigue, nausea/emesis, and pain), six single-items (dyspnea, sleep disturbance, appetite loss, constipation, diarrhea, and financial impact), along with a global QoL score [Aaronson 1993]. Higher scores on the functioning domains and the overall QoL domain correspond with better functioning whereas higher scores on the symptom domains correspond with poorer functioning. During validation studies, over 80% of women were able to complete the EORTC QLQ-C30 and QLQ-CX24 in less than 15 minutes. For estimation of effect sizes in this trial, we will use the data from the validation study of the QLQ-CX24 cited in Greimel [Greimel 2006]. Although a minimal important difference has not been established for this specific module, we will use 7 points (1/2 a standard deviation unit) as an indicator of meaningful clinical difference, as has been done in comparable studies [Norman 2003; Sloan 2006].

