14.6 Analysis for Quality of Life

The quality of life and sexual health of patients in this study will be assessed by respectively EORTC QLQ-C30 core questionnaire with its module QLQ-CX24, the Female Sexual Function Index (FSFI), and the Female Sexual Distress Scale (FSDS-R). The EORTC QLQ-C30 and QLQ-CX24 are self-administered cancer specific questionnaires with multi-dimensional scales. QLQ-C30 consists of both multi-item scales and single item measures, including five functional domains, a global quality of life domain, three symptom domains, and six single items, while QLQ-CX24 has three multi-item subscales: symptom experience, body Image, and sexual/vaginal functioning, and five single items pertaining to menopausal symptoms, lymphedema, lower back pain, tingling and numbness, and sexual enjoyment. FSFI is a 19-item self-report measure of female sexual function that provides scores on six domains of sexual function (desire, arousal, lubrication, orgasm, satisfaction, and pain) as well as a total score. The FSDS-R is a 13-item unidimensional measure of sexually-related distress. Scoring of the quality of life and sexual health data will be completed following the procedures recommended by the EORTC Study Group on Quality of Life and other published algorithms.

The quality of life and sexual health data will be analyzed to look for statistically and clinically significant differences between two treatment arms. Questionnaire compliance rates will first be ascertained for each group at each measurement time point. Mean scores at baseline and the change scores from baseline at each follow-up assessment time point will be calculated for each subscale and summary scores and compared between two arms by Wilcoxon test. The profile of change scores over time between two treatment arms will be compared using linear mixed models.

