	Not At All	A Little	Quite a Bit	Very Much
--	------------------------------	----------------------------	-------------------------------	-----------------------------

45. Have you felt physically less attractive as a result of your disease or treatment?	1	2	3	4
--	---	---	---	---

46. Have you felt less feminine as a result of your disease or treatment?	1	2	3	4
---	---	---	---	---

47. Have you felt dissatisfied with your body?	1	2	3	4
--	---	---	---	---

During the past 4 weeks:

	Not At All	A Little	Quite a Bit	Very Much
--	------------------------------	----------------------------	-------------------------------	-----------------------------

48. Have you worried that sex would be painful?	1	2	3	4
---	---	---	---	---

49. Have you been sexually active?	1	2	3	4
------------------------------------	---	---	---	---

Answer the following questions only if you have been sexually active during the past 4 weeks:

	Not At All	A Little	Quite a Bit	Very Much
--	------------------------------	----------------------------	-------------------------------	-----------------------------

50. Has your vagina felt dry during sexual activity?	1	2	3	4
--	---	---	---	---

51. Has your vagina felt short?	1	2	3	4
---------------------------------	---	---	---	---

52. Has your vagina felt tight?	1	2	3	4
---------------------------------	---	---	---	---

53. Have you felt pain during sexual intercourse or any other sexual activity?	1	2	3	4
--	---	---	---	---

54. Was sexual activity enjoyable to you?	1	2	3	4
---	---	---	---	---

Please check to make sure you have answered all the questions.

Please fill in your initials to indicate that you have completed this questionnaire: _____

Today's date (Year, Month, Day): _____

Thank you.

Sexual Health Questionnaire (FSDS-R & FSFI) – ENGLISH

CCTG Trial: **CX.5**

This **page** to be completed by the Clinical Research Associate

Patient Information

CCTG Patient Serial No: _____

Patient Initials: _____
(first-middle-last)

Institution: _____

Investigator: _____

Scheduled time to obtain quality of life assessment: please check (3)

- Prior to randomization
- At the time of first recurrence

After surgery prior to recurrence:

- 3 months 6 months 12 months
- 24 months 36 months
- Other _____ (specify)

Were ALL questions answered? ___ Yes ___ No If no, reason: _____

Was assistance required? ___ Yes ___ No If yes, reason: _____

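### The SAP's formulas for QLQ-CX24 Sexual Activity and Sexual Enjoyment run in the opposite direction to the one the protocol states

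*SAP*

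**What the plan says.** SAP 7.8.1.2 gives the scoring for the cervical cancer module. Two single items carry a reversing formula: "Sexual Activity $(1 - (Q49-1)/3) * 100" and "Sexual Enjoyment $(1 - (Q54-1)/3) * 100". The other scores in that list are not reversed, for example "Lymphoedema $(Q38-1)/3 * 100".

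Protocol 2.5.4 describes the direction of the module: "Higher scores correspond to worse symptoms except for items 49 and 54".

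The questionnaire in Protocol Appendix VI words item 49 as "Have you been sexually active" and item 54 as "Was sexual activity enjoyable to you". Both have four response categories, from 1 for not at all to 4 for very much.

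On method, Protocol 14.6 states: "Scoring of the quality of life and sexual health data will be completed following the procedures recommended by the EORTC Study Group". The SAP does not say what a high score means on either item, and the shells of Tables 43–45 carry no footnote on direction.

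**The concern.** The raw answer to each of these questions already rises with activity or enjoyment. Subtracting the rescaled answer from 1 turns it round, so the score falls as the woman reports more activity or more enjoyment. That makes a high score the worse state for these items too, which is what the protocol says they are exempt from.

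The practical risk is a reversed reading. The scores keep positive names, and the same report will present the FSFI, where Protocol 2.5.4 says higher means better function. If simple hysterectomy preserved enjoyment better, the FSFI satisfaction domain would favour it, while the QLQ-CX24 enjoyment score would show a negative arm effect. Patient-reported sexual health is a stated secondary objective of the trial, so a sign error here could reach the published conclusions.

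**Working it through.** The question is one of direction, so there is no stated figure to reproduce. The check is to evaluate the SAP formula at every permitted answer and compare it with the unreversed form.

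**Inputs.** Response codes 1 to 4 (Protocol Appendix VI); the SAP formula S = (1 − (Q − 1)/3) × 100 (SAP 7.8.1.2); the unreversed form U = (Q − 1)/3 × 100, which the SAP uses for the module's symptom items.

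| Answer to item 49 or 54 | Q | S (SAP) | U (unreversed) |
|---|---|---|---|
| Not at all | 1 | 100 | 0 |
| A little | 2 | 66.7 | 33.3 |
| Quite a bit | 3 | 33.3 | 66.7 |
| Very much | 4 | 0 | 100 |

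In every row S + U = 100, so S = 100 − U.

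**Effect on the planned analyses.**

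- Baseline mean (Table 43): mean S = 100 − mean U, a reflection about 50.
- Change from baseline (Table 44): (100 − U at follow-up) − (100 − U at baseline) = −(change in U).
- Difference between arms in mean score or mean change: −(difference in U). A true difference of +10 becomes −10.
- Mixed model for change scores (Table 45): every fixed-effect coefficient changes sign, with the same standard error.
- P-values: unchanged for the two-sided Wilcoxon test, because the ranks are simply reversed, and for the mixed model, because the transformation is linear.

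A small invented example shows the sign change. Suppose four women in the simple arm answer 3, 4, 3, 2 (mean 12/4 = 3.00) and four in the radical arm answer 2, 2, 1, 2 (mean 7/4 = 1.75). The unreversed difference is (3.00 − 1.75)/3 × 100 = +41.7; the SAP formula gives −41.7.

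**Comparison with the SAP's own practice.** SAP 7.8.1.1 uses the reversing form for the QLQ-C30 functional scales, for example "Role functioning: $(1 - ((Q6+Q7)/2 - 1)/3) * 100". Those items ask about trouble or limitation, with 4 the worst answer, so reversal makes higher mean better. Global health status, from items 29 and 30, runs from very poor at 1 to excellent at 7, and the SAP leaves it unreversed because it already points upward. Items 49 and 54 have the orientation of global health status but receive the treatment of the functional scales.

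**The case against.** The best defence is that the reversal is deliberate. The protocol sentence names items, not scales, and stands in a description of the instrument. It can be read as saying that these two questions are worded the other way round, which would be a reason to turn them so that the whole module points in one direction. The SAP reverses exactly these two module items and no others, and with them reversed every QLQ-CX24 score in the list runs from better to worse. A positive name is not decisive either: Sexual/Vaginal Functioning is built from dryness, shortness, tightness and pain, so it too is worse when higher.

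Part of this stands. The names alone do not prove an error, and the formulas are a coherent convention in themselves. But the SAP nowhere states that convention, and the protocol sentence is about what higher scores mean, so on its plain reading the SAP removes the exception. Even if alignment was intended, the direction would have to be written down and the protocol sentence reconciled with it.

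The objections on importance also stand. These are two unpowered single items among many patient-reported scores, and sexual activity is not among the five single items that either document lists in its description of the module. The powered comparisons and the three key hypotheses rest on the QLQ-CX24 symptom outcomes, the FSDS-R total and the FSFI total, none of which uses item 49 or 54. No decision rule depends on them.

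**Conclusion.** The concern holds. Followed as written, SAP 7.8.1.2 gives Sexual Activity and Sexual Enjoyment scores whose direction is the reverse of what Protocol 2.5.4 states. The inversion is complete: 0 in place of 100 at one end of the scale and 100 in place of 0 at the other, with the sign of every change score and arm effect flipped. Magnitudes and p-values are unaffected, so a significant result would carry the right p-value and the opposite sign.

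This rests on the item wording and coding in Appendix VI and on reading the protocol sentence as a statement about scores. The EORTC scoring manual is not among the documents and was not relied on. The reach is limited to two secondary single items; the primary endpoint and the key quality-of-life hypotheses are untouched. It should be corrected before the patient-reported outcome tables are produced.

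**What to change.** In SAP 7.8.1.2, score item 49 as (Q49 − 1)/3 × 100 and item 54 as (Q54 − 1)/3 × 100, and state that for these two scores higher means more activity or more enjoyment. Add the same statement as a footnote to Tables 43, 44 and 45; since the other QLQ-CX24 scores run the other way, the footnote should give the direction of each. Because Protocol 14.6 commits to EORTC-recommended scoring, the sponsor should confirm the corrected formulas against that source when making the edit.

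The cost is two formula edits, one sentence and a footnote, plus the matching lines of the scoring program. No new data are needed and no other analysis changes.

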7.8.1.3 FSFI

The FSFI is a 19-item self-report measure of female sexual function that provides scores on six domains of sexual function (desire, arousal, lubrication, orgasm, satisfaction and pain) as well as a total score:

- Desire $(Q1+Q2) * 0.6$
- Arousal $(Q3+...+Q6) * 0.3$
- Lubrication $(Q7+...+Q10) * 0.3$
- Orgasm $(Q11+...+Q13) * 0.4$
- Satisfaction $(Q14+...+Q16) * 0.4$
- Pain $(Q17+...+Q19) * 0.4$
- Total Score $(Q1+...+Q19) / 19 * 1.2$

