Sexual distress is what motivates individuals to seek treatment for sexual difficulties. Given this, and given the finding that changes in genital sensations/arousal are considered to be the primary source of symptom-associated distress following surgical treatment of cervical cancer, sexual distress will be considered our primary outcome and overall sexual functioning as a secondary outcome within the sexual health analyses [Bergmark 2002].

The FSFI [Rosen 2000] is a validated measure of sexual desire, orgasm, lubrication, pain, and satisfaction widely available in a variety of languages. It is a 19-item self-report measure of female sexual function that provides scores on six domains of sexual function as well as a total score. Domains include: Desire (2 items), Arousal (4 items), Lubrication (4 items), Orgasm (3 items), Satisfaction (3 items), and Pain (3 items). Items are scored on a 5-point Likert scale with higher scores corresponding with better sexual functioning. The FSFI has been shown to reliably discriminate women with Female Sexual Arousal Disorder from sexually-healthy controls on each of the six domains of sexual function as well as the Full Scale score [Rosen 2000]. The FSFI was found to be internally consistent (Cronbach's alpha ranged between 0.82 and 0.98;) and test-retest reliabilities using a 4-week interval ranged between $r = 0.79$ and 0.86 [Rosen 2000].

The FSDS-R [Derogatis 2002, Dergogatis, 2008] is a 13-item measure of sexually-related distress available in English and French. Items are scored on a 5-point Likert scale. Scores range from 0 – 48, where higher scores represent higher levels of sexual distress. The FSDS-R has been shown to have good discriminant validity for differentiating between sexually dysfunctional and sexually functional women [Derogatis 2002, Dergogatis, 2008]. There is also satisfactory consistency, test-retest reliability, and moderate correlations with measures of nonsexual distress.

Table 1: Quality Of Life Instruments (in addition to the Global Quality of Life instrument EORTC QLQ-C30)

Instrument	Estimated mean baseline	Estimated change with simple hyst.	Estimated change with radical hyst.	Difference we wish to test for (delta) i.e. the differential between arms	Estimated pooled std deviation of the scores
EORTC CX.24 symptom subscale	3	+3 (mean score 6)	+10 (mean score 13)	7	13.5
FSDS-R total score	22*	+5	+10	5	10
FSFI Total Score	33.3*	-5	-10** (mean score 23)	5	21

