Sexual activity can include caressing, foreplay, masturbation, and vaginal intercourse.

Sexual intercourse is defined as penile penetration (entry) of the vagina.

Sexual stimulation includes situations like foreplay with a partner, self-stimulation (masturbation), or sexual fantasy.

Sexual desire or interest is a feeling that includes wanting to have a sexual experience, feeling receptive to a partner's sexual initiation, and thinking or fantasizing about having sex.

Sexual arousal is a feeling that includes both physical and mental aspects of sexual excitement. It may include feelings of warmth or tingling in the genitals, lubrication (wetness), or muscle contractions.

Circle only one item per question.

Question	Response options (please circle)
1. Over the past 4 weeks, how satisfied have you been with your overall sexual life?	5 = Very satisfied 4 = Moderately satisfied 3 = About equally satisfied & dissatisfied 2 = Moderately dissatisfied 1 = Very dissatisfied
2. Over the past 4 weeks, how often did you feel sexual desire or interest?	5 = Almost always or always 4 = Most times (more than ½ the time) 3 = Sometimes (about ½ the time) 2 = A few times (less than ½ the time) 1 = Almost never or never
3. Over the past 4 weeks, how would you rate your level (degree) of sexual desire or interest?	5 = Very high 4 = High 3 = Moderate 2 = Low 1 = Very low or none at all

Question

Response options (please circle)

- | | |
|---|---|
| 4. Over the past 4 weeks, did you engage in sexual activity of any kind with a partner and/or by yourself (masturbation)? | 0 = No sexual activity (neither with a partner nor by myself) |
| | 1 = Sexual activity with a partner only |
| | 1 = Sexual activity by myself only |
| | 1 = Sexual activity both with a partner and by myself |

If you selected “0 = No sexual activity (neither with a partner nor by myself)”, please skip remaining questions on this questionnaire. If you selected any other response, please continue.

- | | |
|--|--|
| 5. Over the past 4 weeks, how often did you feel sexually aroused (“turned on”) during sexual activity or intercourse? | X = No sexual activity |
| | 5 = Almost always or always |
| | 4 = Most times (more than ½ the time) |
| | 3 = Sometimes (about ½ the time) |
| | 2 = A few times (less than ½ the time) |
| | 1 = Almost never or never |

- | | |
|--|-----------------------------|

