13. Over the past 4 weeks, when you had sexual stimulation, how often did you reach orgasm (climax)?	X = No sexual activity 5 = Almost always or always 4 = Most times (more than ½ the time) 3 = Sometimes (about ½ the time) 2 = A few times (less than ½ the time) 1 = Almost never or never
14. Over the past 4 weeks, when you had sexual stimulation, how difficult was it you to reach orgasm (climax)?	X = No sexual activity 1 = Extremely difficult or impossible 2 = Very difficult 3 = Difficult 4 = Slightly difficult 5 = Not difficult
15. Over the past 4 weeks, how satisfied were you with your ability to reach orgasm (climax) during sexual activity or intercourse?	X = No sexual activity 5 = Very satisfied 4 = Moderately satisfied 3 = About equally satisfied & dissatisfied 2 = Moderately dissatisfied 1 = Very dissatisfied

This box to be completed by the clinical research associate: Pt. Serial #: _____ Pt. Initials: _____

Question

Response options (please circle)

- | | |
|--|--|
| 16. Over the past 4 weeks, how satisfied have you been with the amount of emotional closeness during sexual activity between you and your partner? | X = No partner
5 = Very satisfied
4 = Moderately satisfied
3 = About equally satisfied & dissatisfied
2 = Moderately dissatisfied
1 = Very dissatisfied |
| 17. Over the past 4 weeks, how satisfied have you been with your sexual relationship with your partner? | X = No partner
5 = Very satisfied
4 = Moderately satisfied
3 = About equally satisfied & dissatisfied
2 = Moderately dissatisfied
1 = Very dissatisfied |
| 18. Over the past 4 weeks, how often did you experience discomfort or pain following vaginal penetration? | X = Did not attempt penetration
5 = Almost always or always
4 = Most times (more than ½ the time)
3 = Sometimes (about ½ the time)
2 = A few times (less than ½ the time)
1 = Almost never or never |
| 19. Over the past 4 weeks, how often did you experience discomfort or pain during vaginal penetration? | X = Did not attempt penetration
5 = Almost always or always
4 = Most times (more than ½ the time)
3 = Sometimes (about ½ the time)
2 = A few times (less than ½ the time)
1 = Almost never or never |
| 20. Over the past 4 weeks, how would you rate your level (degree) of discomfort or pain during or following vaginal penetration? | X = Did not attempt penetration
5 = Very high
4 = High
3 = Moderate
2 = Low
1 = Very low or none at all. |

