7.8.1.4 FSDS-R

The FSDS-R is a 13-item unidimensional measure of sexual-related distress.

- Total Score $Q1+...+Q13$

For all the above PRO questionnaire, missing items in a multiitem scale will be handled by the following methods: Values will be imputed for missing items by “assuming that the missing items have values equal to the average of those items which are present” for the total score in which at least half the items are completed. The total score will be treated as missing if less than half of the items are completed.

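### The FSFI formulas in SAP 7.8.1.3 do not fit the administered form: the total is off the planning scale, items fall in the wrong domains, and pain is not reversed

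*SAP*

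**What the plan says.** SAP 7.8 introduces the scoring section by defining Q_i as "denoting the i -th question in the PRO questionnaire". SAP 7.8.1.3 then takes the FSFI in consecutive blocks: desire Q1–Q2 (×0.6), arousal Q3–Q6 (×0.3), lubrication Q7–Q10 (×0.3), orgasm Q11–Q13, satisfaction Q14–Q16 and pain Q17–Q19 (each ×0.4). The total is "Total Score $(Q1+...+Q19) / 19 * 1.2". No item is reversed and no item map is given.

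Protocol 2.5.4 describes a 19-item instrument with domains of 2, 4, 4, 3, 3 and 3 items, "higher scores corresponding with better sexual functioning". Table 1 there plans an FSFI total of 33.3 at baseline, changes of −5 (simple) and −10 (radical, to a mean of 23), and a difference of 5 between arms.

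The form in Protocol Appendix VI has 20 numbered items. Item 1 asks "how satisfied have you been with your overall sexual life". Item 4 asks whether there was any sexual activity, is coded 0/1, and tells women answering 0: "please skip remaining questions on this questionnaire". Item 20 asks "how would you rate your level (degree) of discomfort or pain", with 5 for very high and 1 for very low or none. Items 18 and 19 likewise give 5 to the most frequent pain.

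The missing-item rule in SAP 7.8.1.4 covers all the questionnaires: "The total score will be treated as missing if less than half of the items are completed".

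**The concern.** Three things look wrong. The total cannot take the values the protocol planned for it. The SAP's item numbers, taken as defined, do not line up with the form. Pain enters with the opposite sign to every other domain.

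The FSFI total is the measure for quality-of-life Hypothesis 3 in Protocol 2.5.3, and its domains carry the exploratory hypotheses. SAP Tables 44 and 45 report means and mixed-model estimates in score units. Code written from 7.8.1.3 and run on the form's own numbers and codes would mix constructs within every domain. It would also count pain as good function, which works against the benefit expected from simple hysterectomy. The reported total could not be set directly beside 33.3, 23 or the 5-point difference.

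**Working it through.** **The plan's own sample size.** Protocol 14.6 asks for 560 women to detect 5 points with SD 21, 80% power and two-sided 0.05. (It prints the distress scale twice; 21 and 5 are the FSFI row of Table 1.) The two-sample normal formula n = 2(z₀.₉₇₅ + z₀.₈₀)²·SD²/δ² gives 2 × 7.849 × 441/25 = 276.9, so 277 per arm and 554 in total (556 with the t distribution). This agrees with 560. Dividing both δ and SD by 6 leaves it at 554, so a pure change of scale does not affect the planned number.

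**1. Scale of the total.** With items scored 1 to 5:
- SAP total: minimum 1 × 1.2 = 1.2, maximum 5 × 1.2 = 6.0, a span of 4.8.
- SAP domains: each has minimum 2 × 0.6 = 4 × 0.3 = 3 × 0.4 = 1.2 and maximum 10 × 0.6 = 20 × 0.3 = 15 × 0.4 = 6. The six sum to 7.2–36.

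The planned 33.3 and 23 lie above the SAP maximum, and the planned falls of 5 and 10 both exceed its span. All fit on 7.2–36.

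The SAP total is also not the domain sum divided by six. It weights desire 2/19 = 10.5%, arousal and lubrication 4/19 = 21.1% each, and the other three 3/19 = 15.8% each, against 16.7% per domain. Take two profiles of domain item means, in the SAP's domain order with pain already recoded: 5,3,3,4,4,4 and 1,5,5,4,4,4. Both have a domain sum of 23 × 1.2 = 27.6. Their SAP totals are 70/19 × 1.2 = 4.42 and 78/19 × 1.2 = 4.93.

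**2. Item map, reading Q_i as the i-th item on the form.**

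| Domain | SAP items | What the form holds there | Correct |
|---|---|---|---|
| Desire | 1–2 | satisfaction, desire | 1/2 |
| Arousal | 3–6 | desire, activity question, arousal, arousal | 2/4 |
| Lubrication | 7–10 | arousal, arousal, lubrication, lubrication | 2/4 |
| Orgasm | 11–13 | lubrication, lubrication, orgasm | 1/3 |
| Satisfaction | 14–16 | orgasm, orgasm, satisfaction | 1/3 |
| Pain | 17–19 | satisfaction, pain, pain | 2/3 |

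That is 9 of 19. Item 15 (satisfaction with ability to reach orgasm) is counted as orgasm, as the protocol's three orgasm and three satisfaction items require. Item 20 is never used. Because item 4 is at most 1, arousal cannot exceed (5 + 1 + 5 + 5) × 0.3 = 4.8, and the total cannot exceed (18 × 5 + 1)/19 × 1.2 = 5.75.

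**3. Direction, using the printed codes.** Take a woman with every function item at 5 and item 4 = 1.

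| | SAP pain | SAP total | Corrected total |
|---|---|---|---|
| No pain (items 18–20 = 1) | (5+1+1) × 0.4 = 2.8 | (80+1+2)/19 × 1.2 = 5.24 | 36.0 |
| Maximal pain (items 18–20 = 5) | (5+5+5) × 0.4 = 6.0 | (80+1+10)/19 × 1.2 = 5.75 | 31.2 |

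One category less pain on all three items lowers the SAP pain score by 2 × 0.4 = 0.8 and the SAP total by 2/19 × 1.2 = 0.13. Corrected scoring raises both by 3 × 0.4 = 1.2.

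**Inactive women.** A woman answering 0 at item 4 has completed items 1–4: 4 of the SAP's 19 items, or 3 of 19 once item 4 is left out. She has no total under the half-items rule. If that rule were applied by domain, she would have two of the four SAP arousal items (3 and 4). With item 3 = r, her imputed arousal score is (r/2) × 4 × 0.3 = 0.6r, or 0.6 to 3.0, built from one desire item and the activity question.

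**The case against.** The strongest reply is that the SAP calls the FSFI a 19-item measure and numbers Q1–Q19 in blocks that match the protocol's domain order and sizes. That looks like formulas for a 19-item order without the activity question, and the database may already be renumbered and pain recoded. Protocol 14.6 also commits scoring to published algorithms. This makes parts 2 and 3 conditional on the form's numbers and codes being used. It does not remove them. Neither document states a renumbering or recode, and SAP 7.8 defines the numbering literally. The QLQ-CX24 formulas in 7.8.1.2 use the form's printed numbers, and the SAP writes its reversals out elsewhere. A general reference to published algorithms does not override explicit formulas.

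Second, multiplying the SAP total by 6 restores the range, and rescaling alone changes neither Wilcoxon ranks nor sample size. That is correct, but the weights stay wrong. The two profiles above, equal on the domain sum, would still differ by (78 − 70)/19 × 7.2 = 3.0 points, against a planned difference of 5. The example is an extreme one.

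Third, items 5–20 allow an X response (no activity, no partner or no penetration attempted), which a corrected formula must also handle. An active woman with X on items 16–20 has 14 of 19 items answered but no pain item. The SAP's averaging rule for missing items largely covers this, provided X is declared missing.

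Finally, the stakes are limited. The FSFI ranks below the distress scale within sexual health and belongs to an optional component.

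**Conclusion.** The concern holds. The total in 7.8.1.3 cannot represent the planned FSFI values and is not the sum of the SAP's own domains, whatever numbering or coding the database uses. Read as SAP 7.8 defines its item numbers, only 9 of 19 slots are right, and with the printed codes pain carries the wrong sign (5.24 without pain, 5.75 with maximal pain). Those last two results assume literal numbering, raw codes and all items answered; neither document states anything different. The effect is confined to the FSFI total and domains. The primary endpoint, the distress scale and the planned sample size are untouched. It should be fixed before the FSFI is scored.

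**What to change.** Rewrite SAP 7.8.1.3 for the administered form, with subscripts as printed in Appendix VI:

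- Desire: (Q2 + Q3) × 0.6
- Arousal: (Q5 + … + Q8) × 0.3
- Lubrication: (Q9 + … + Q12) × 0.3
- Orgasm: (Q13 + Q14 + Q15) × 0.4
- Satisfaction: (Q1 + Q16 + Q17) × 0.4
- Pain: [(6 − Q18) + (6 − Q19) + (6 − Q20)] × 0.4
- Total: the sum of the six domains; Q4 is not scored.

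If the database already holds renumbered or recoded items, state that mapping instead; the total still needs to become the domain sum. State that X is treated as missing, that pain is reversed before any averaging, and whether the half-items rule applies to the 19 items or within domains.

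As a secondary point, say that women answering 0 at item 4 have no FSFI total, and report item 4 by randomized arm beside the FSFI results. This does not restore their scores, and QLQ-CX24 item 49 already records sexual activity, but it shows whom the comparison leaves out.

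The cost is SAP text and scoring code. No new data are needed.
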